12.4.4 Overall Response Assessment

Table 5: Overall Response Evaluation for Neuroblastoma Patients and MIBG Positive Disease Only

If patients are enrolled without disease measurable by CT/MRI, any new or newly identified lesion by CT/MRI that occurs during therapy would be considered progressive disease.

MIBG	CT/MRI	Bone Scan	Bone Marrow	Catechol	Overall
PD	Any	Any	Any	Any	PD

Any	New Lesion	Any	Any	Any	PD
Any	Any	PD	Any	Any	PD
Any	Any	Any	PD	Any	PD
SD	No New Lesion	Non-PD	Non-PD	Any	SD
PR	No New Lesion	Non-PD	Non-PD	Any	PR
CR	No New Lesion	Non-PD	Non-PD	Elevated	PR
CR	No New Lesion	CR	CR	Normal	CR

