12.2.2 Disease Parameters

12.2.2.1 Measurable disease: Measurable lesions are defined as those that can be accurately measured in at least one dimension (longest diameter to be recorded) as ≥ 20 mm by chest x-ray, as ≥ 10 mm with CT scan, or ≥ 10 mm with calipers by clinical exam. All tumor measurements must be recorded in millimeters (or decimal fractions of centimeters).

Note: Tumor lesions that are situated in a previously irradiated area must show definitive evidence of progression to be considered measurable.

12.2.2.2 Malignant lymph nodes: To be considered pathologically enlarged and measurable, a lymph node must be ≥ 15 mm in short axis when assessed by CT scan (CT scan slice thickness no greater than 5 mm). At baseline and in follow-up, only the short axis will be measured and followed.

12.2.2.3 Non-measurable disease: All other lesions (or sites of disease), including small lesions (longest diameter < 10 mm or pathological lymph nodes with ≥ 10 mm to < 15 mm short axis), are considered non-measurable disease. Bone lesions, leptomeningeal disease, ascites, pleural/pericardial effusions, lymphangitis cutis/pulmonitis, inflammatory breast disease, and abdominal masses (not followed by CT or MRI), are considered as non-measurable.

Note: Cystic lesions that meet the criteria for radiographically defined simple cysts should not be considered as malignant lesions (neither measurable nor non-measurable) since they are, by definition, simple cysts. 'Cystic lesions' thought to represent cystic metastases can be considered as measurable lesions, if they meet the definition of measurability described above. However, if non-cystic lesions are present in the same patient, these are preferred for selection as target lesions.

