- 12.2.3.6 Cytology, Histology: These techniques can be used to differentiate between partial responses (PR) and complete responses (CR) in rare cases (e.g., residual lesions in tumor types, such as germ cell tumors, where known residual benign tumors can remain).

Cytology should be obtained if an effusion appears or worsens during treatment when the measurable tumor has met criteria for response or stable disease.

- 12.2.3.7 FDG-PET: While FDG-PET response assessments need additional study, it is sometimes reasonable to incorporate the use of FDG-PET scanning to complement CT scanning in assessment of progression (particularly possible 'new' disease). New lesions on the basis of FDG-PET imaging can be identified according to the following algorithm:
- a. Negative FDG-PET at baseline, with a positive FDG-PET at follow-up is a sign of PD based on a new lesion.
 - b. No FDG-PET at baseline and a positive FDG-PET at follow-up: If the positive FDG-PET at follow-up corresponds to a new site of

disease confirmed by CT, this is PD. If the positive FDG-PET at follow-up is not confirmed as a new site of disease on CT, additional follow-up CT scans are needed to determine if there is truly progression occurring at that site (if so, the date of PD will be the date of the initial abnormal FDG-PET scan). If the positive FDG-PET at follow-up corresponds to a pre-existing site of disease on CT that is not progressing on the basis of the anatomic images, this is not PD.

Note: A 'positive' FDG-PET scan lesion means one that is FDG avid with an uptake greater than twice that of the surrounding tissue on the attenuation corrected image.

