12.2.4.2 Evaluation of Non-Target Lesions

Complete Response (CR): Disappearance of all non-target lesions and normalization of tumor marker level. All lymph nodes must be non-pathological in size (<10 mm short axis)

Note: If tumor markers are initially above the upper normal limit, they must normalize for a patient to be considered in complete clinical response.

Non-CR/Non-PD: Persistence of one or more non-target lesion(s) and/or maintenance of tumor marker level above the normal limits

Progressive Disease (PD): Appearance of one or more new lesions and/or *unequivocal progression* of existing non-target lesions. *Unequivocal progression* should not normally trump target lesion status. It must be representative of overall disease status change, not a single lesion increase.

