12.2.5 Overall Response Assessment

Table 1: For Patients with Measurable Disease (i.e., Target Disease)

Target Lesions	Non-Target Lesions	New Lesions	Overall Response	Best Overall Response when Confirmation is Required*
CR	CR	No	CR	≥ 28 days Confirmation
CR	Non-CR/Non-PD	No	PR	≥ 28 days Confirmation
CR	Not evaluated	No	PR	
PR	Non-CR/Non-PD/not evaluated	No	PR	
SD	Non-CR/Non-PD/not evaluated	No	SD	documented at least once ≥ 28 days from baseline
PD	Any	Yes or No	PD	no prior SD, PR or CR
Any	PD**	Yes or No	PD	
Any	Any	Yes	PD	

* See RECIST 1.1 manuscript for further details on what is evidence of a new lesion.
 ** In exceptional circumstances, unequivocal progression in non-target lesions may be accepted as disease progression.
Note: Patients with a global deterioration of health status requiring discontinuation of treatment without objective evidence of disease progression at that time should be reported as “*symptomatic deterioration.*” Every effort should be made to document the objective progression even after discontinuation of treatment.

Table 2: For Patients with Non-Measurable Disease (i.e., Non-Target Disease)

Non-Target Lesions	New Lesions	Overall Response
CR	No	CR
Non-CR/non-PD	No	Non-CR/non-PD*
Not all evaluated	No	not evaluated
Unequivocal PD	Yes or No	PD
Any	Yes	PD
* ‘Non-CR/non-PD’ is preferred over ‘stable disease’ for non-target disease since SD is increasingly used as an endpoint for assessment of efficacy in some trials so to assign this category when no lesions can be measured is not advised		

Table 4: Overall Response for Patients with Neuroblastoma and Measurable Disease

CT/MRI	MIBG	Bone Scan	Bone Marrow	Catechol	Overall
PD	Any	Any	Any	Any	PD
Any	PD	Any	Any	Any	PD
Any	Any	PD	Any	Any	PD
Any	Any	Any	PD	Any	PD
SD	CR/PR/SD	Non-PD	Non-PD	Any	SD
PR	CR/PR	Non-PD	Non-PD	Any	PR
CR/PR	PR	Non-PD	Non-PD	Any	PR
CR	CR	Non-PD	Non-PD	Elevated	PR
CR	CR	CR	CR	Normal	CR

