12.3.2 Complete Response

Disappearance of all evaluable disease.

- 12.3.3 Partial response
Partial responses cannot be determined in patients with evaluable disease
- 12.3.4 Stable Disease (SD)
That which does not qualify as Complete Response (CR), Partial Response (PR), or Progressive Disease.
- 12.3.5 Progressive Disease
The appearance of one or more new lesions or evidence of laboratory, clinical, or radiographic progression.
- 12.3.6 Overall Best Response Assessment
Each patient will be classified according to his “best response” for the purposes of analysis of treatment effect. Best response is determined as outlined in [Section 12.6](#) from a sequence of overall response assessments.

12.4 **Response Criteria for Neuroblastoma Patients with MIBG Positive Lesions**

- 12.4.1 MIBG Positive Lesions
Patients who have a positive MIBG scan at the start of therapy will be evaluable for MIBG response. The use of ^{123}I for MIBG imaging is recommended for all scans. If the patient has only one MIBG positive lesion and that lesion was radiated, a biopsy must be done at least 28 days after radiation was completed and must show viable neuroblastoma.
- 12.4.2 The following criteria will be used to report MIBG response by the treating institution:
- Complete response: Complete resolution of all MIBG positive lesions
Partial Response: Resolution of at least one MIBG positive lesion, with persistence of other MIBG positive lesions
Stable disease: No change in MIBG scan in number of positive lesions
Progressive disease: Development of new MIBG positive lesions
- 12.4.3 The response of MIBG lesions will be assessed on central review using the Curie scale¹⁴ as outlined below. Central review responses will be used to assess efficacy for study endpoint. See [Section 8.2](#) for details on transferring images to the Imaging Research Center.

[figure not shown]
NOTE: This scoring should also be done by the treating institution for end of course response assessments.

The body is divided into 9 anatomic sectors for osteomedullary lesions, with a 10th general sector allocated for any extra-osseous lesion visible on MIBG scan. In each region, the lesions are scored as follows. The **absolute extension score** is graded as:

0 = no site per segment,

- 1 = 1 site per segment,
- 2 = more than one site per segment,
- 3 = massive involvement (>50% of the segment).

The **absolute score** is obtained by adding the score of all the segments. See diagram of sectors below:

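### Table 5 (12.4.4) cannot register progression or persistence of non-measurable CT/MRI lesions in MIBG-positive neuroblastoma, and so conflicts with 12.2.1.2, Table 2, 12.3.2 and 12.3.5

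*Combined protocol and SAP*

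**What the plan says.** Table 5 is titled "Overall Response Evaluation for Neuroblastoma Patients and MIBG Positive Disease Only". The sentence beneath the title sets a different condition, "If patients are enrolled without disease measurable by CT/MRI", and continues that "any new or newly identified lesion by CT/MRI that occurs during therapy would be considered progressive disease". The CT/MRI column contains *New Lesion*, *No New Lesion* and the wildcard *Any*. The SD row, both PR rows and the CR row all carry *No New Lesion*.

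Elsewhere in Section 12:

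- **12.2.2.3** counts as non-measurable disease "small lesions (longest diameter < 10 mm or pathological lymph nodes with ≥ 10 mm to < 15 mm short axis").
- **12.2.1.2** assesses baseline lesions that are evaluable but not measurable by whether they are present, absent or unequivocally progressing.
- **12.2.4.2** defines PD of non-target lesions as the appearance of one or more "new lesions and/or *unequivocal progression* of existing non-target lesions". **Table 2** carries unequivocal PD of non-target disease through to overall PD.
- **12.3.5** defines PD for evaluable disease as "The appearance of one or more new lesions or evidence of laboratory, clinical, or radiographic progression".
- **12.3.2** allows CR in evaluable disease only when all of it has gone.
- **Table 4**, "Overall Response for Patients with Neuroblastoma and Measurable Disease", grades CT/MRI as CR, PR, SD or PD and requires CT/MRI CR for overall CR.

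**The concern.** Having no measurable CT/MRI disease is not the same as having no CT/MRI disease. Section 4.1.5 admits patients with evaluable disease only. A child with MIBG-positive disease and a small nodule or a borderline node therefore meets the Table 5 lead-in while carrying a visible CT/MRI lesion. For that child the column asks whether something new has appeared, but not what has happened to what was already there.

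Two assessors could read the same scans, each follow a section of the protocol, and record different categories: one PD under 12.3.5, the other SD or PR under Table 5. Antitumor activity is secondary aim 1.2.1, and best response (12.6) is built from these overall assessments. Progression status is also used outside the response report. Section 10.1.a refers to Section 12.0 for progressive disease, and section 5.2 requires at least stable disease before a further cycle.

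**Working it through.** The plan gives no figure to reproduce here, so the check applies Table 5 as a decision rule and compares it with the other sections.

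**1. Does another column catch growth?** MIBG PD means new MIBG-positive lesions only, both in the institutional criteria (12.4.2) and on central review (12.4.3). Growth of an existing lesion therefore does not produce MIBG PD. Bone scan and marrow do not assess soft tissue, and the catecholamine column never leads to PD.

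**2. Enumeration of Table 5.** Inputs: MIBG (PD, SD, PR, CR); CT/MRI (new, no new); bone scan (PD, CR, other non-PD); marrow (same three); catecholamines (elevated, normal).

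- All combinations: 4 × 2 × 3 × 3 × 2 = 144.
- No PD in any column and no new CT/MRI lesion: 3 × 1 × 2 × 2 × 2 = 24. The other 144 − 24 = 120 are PD.

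| MIBG | Condition | Combinations | Overall |
|---|---|---|---|
| SD | any non-PD | 8 | SD |
| PR | any non-PD | 8 | PR |
| CR | catecholamines elevated | 4 | PR |
| CR | bone scan CR, marrow CR, catecholamines normal | 1 | CR |
| CR | catecholamines normal, bone scan and/or marrow not CR | 3 | no matching row |

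The total is 8 + 12 + 1 + 3 = 24. These count table entries, not patients. The three unmatched entries are a separate gap.

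**3. Existing CT/MRI lesions.** A lesion that has progressed, one that is unchanged and one that has resolved all enter as *No New Lesion*, so all three give the same 24 results.

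**4. Side by side.**

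| Existing non-measurable CT/MRI disease | Table 5 | Other sections |
|---|---|---|
| Unequivocal progression | SD, PR or CR | PD (Table 2, 12.3.5; assessed as such in 12.2.1.2) |
| Persists, not MIBG-avid, all else clear | CR | not CR (12.3.2, 12.2.4.2) |

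**5. Effect of aligning Table 5.** With progression of existing disease entered as PD, all 24 results for a progressing lesion become PD. With CR requiring disappearance, a persisting lesion keeps 8 SD and 12 PR. Its single CR entry then needs a stated outcome. Results for patients with no CT/MRI lesion, or with a resolved one, do not change.

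**The case against.** **The title limits the table to MIBG-positive disease only.** On that reading there is no baseline CT/MRI lesion to grow or persist, and a two-state column is complete. This narrows the point: a reader might infer that all neuroblastoma without measurable disease is affected, and the documents do not support that. It does not remove the point. The lead-in says measurable, which lets non-measurable lesions in. If the title governs, a child with both kinds of disease belongs to neither Table 4 nor Table 5. Falling back on 12.3 then changes the available categories, because 12.3.3 says PR cannot be determined there.

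**Other sections already make progression PD.** They do, so it would go too far to say that such a child is certain to be misclassified. But nothing says that those sections override the table written for this disease.

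**A growing single node is not automatically PD.** This stands. A reader might treat one enlarging node or nodule as PD under 12.2.4.2, but that section asks for a change in overall disease status rather than growth of one lesion. The conflict is clearer with 12.2.1.2, Table 2 and 12.3.5.

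**CR with residual disease is a narrow case.** This also stands. It requires a non-avid lesion together with MIBG CR, bone scan CR, marrow CR and normal catecholamines. Section 12.2.3.6 recognises that residual lesions can occasionally be benign.

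**The rule on newly identified lesions.** A reader might infer that a lesion present at baseline is wrongly called PD when first noticed later. The text does not mention pre-existing lesions; the rule is explicit and conservative. The PET rule in 12.2.3.7, under which a pre-existing CT site "that is not progressing on the basis of the anatomic images, this is not PD", concerns a different situation. Changing this rule would be a preference, not a correction.

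**Other safeguards.** Central review (8.2.1) covers responders and long-term stable disease, and 10.1 also allows removal on clinical evidence or physician judgment. These reduce the practical risk, but they do not say which section sets the response category.

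**Conclusion.** The point holds in limited form. For MIBG-positive neuroblastoma with non-measurable CT/MRI lesions at baseline, Table 5 followed as written gives the same answer whether those lesions progress, persist or resolve. That answer conflicts with rules stated elsewhere in Section 12. The defect is an unreconciled contradiction, together with a title and lead-in that do not define the same population.

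The conclusion assumes that the lead-in admits such patients and that an assessor relies on Table 5. The number of neuroblastoma patients is not stated. Excluding known marrow metastatic disease (4.1.9.1) and the minimum BSA (4.1.2) may keep it low.

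A reader might divide one child by the planned enrollment to obtain a shift in a response rate. The documents do not support that calculation: 12.2.1.1 limits objective-response evaluability, apart from early progressors, to patients with measurable disease, and section 11.5 reports response descriptively. No error rate, power or sample size is affected. The correction is still worth making, because a stated rule returns a category that the rest of the section contradicts, and sections 10.1.a and 5.2 depend on progression status. This point takes no position on when treatment should stop; the passages must be reconciled.

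**What to change.** 1. Make the Table 5 title and lead-in describe the same population, and state which section governs MIBG-positive patients who also have non-measurable CT/MRI lesions.
2. If Table 5 governs, change the CT/MRI entry in the PD row to *New lesion, or unequivocal progression of existing non-measurable CT/MRI disease (12.2.1.2, 12.3.5)*, and the entry in the SD and PR rows to *Neither*.
3. In the CR row, require that evaluable CT/MRI disease has disappeared (12.3.2). Add a row giving the outcome when every other column is clear but a CT/MRI lesion persists without progression, since that entry would otherwise have no category.

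The cost is the wording of one title or sentence, one table column and one row. CT/MRI is already an input to Table 5, so no new scans or data are needed. The downside is slightly fewer SD, PR or CR calls.

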12.4.5 Overall Best Response Assessment

Each patient will be classified according to his “best response” for the purposes of analysis of treatment effect. Best response is determined from the sequence of the overall response assessments as described in Table 3 in [Section 12.6](#).

12.5 **Response Criteria for Patients with CNS Tumors**

12.5.1 Measurable Disease

Any lesion that is at minimum 10 mm in one dimension on standard MRI or CT, for CNS tumors.

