3.9 Study Enrollment

Patients may be enrolled on the study once all eligibility requirements for the study have been met. Patients who give informed consent for the protocol in order to undergo screening for eligibility are not considered enrolled and should not be enrolled until the screening is completed and they are determined to meet all eligibility criteria. Study enrollment is accomplished by going to the CTSU OPEN (Oncology Patient Enrollment Network) <https://open.ctsu.org/open/>. For questions, please contact the COG Study Research Coordinator, or the CTSU OPEN helpdesk at <https://www.ctsu.org/CTSUContact.aspx>. Patients must be enrolled before treatment begins. The date protocol therapy is started must be no later than five (5) calendar days after the date of study enrollment. **Patients must not receive any protocol therapy prior to enrollment.**

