4.0 PATIENT ELIGIBILITY

All clinical and laboratory studies to determine eligibility must be performed within 7 days prior to enrollment unless otherwise indicated. Laboratory values used to assess eligibility must be no older than seven (7) days at the start of therapy. Laboratory tests need **not** be repeated if therapy starts **within** seven (7) days of obtaining labs to assess eligibility. If a post-enrollment lab value is outside the limits of eligibility, or laboratory values are older than 7 days, then the following laboratory evaluations must be re-checked within 48 hours prior to initiating therapy: CBC with differential, bilirubin, ALT (SGPT) and serum creatinine. If the recheck is outside the limits of eligibility, the patient may not receive protocol therapy and will be considered off protocol therapy. Imaging studies must be obtained within 14 days prior to start of protocol therapy (repeat the tumor imaging if necessary).

Clarification in timing when counting days: As an example, please note that if the patient's last day of prior therapy is September 1st, and the protocol requires waiting at least 7 days for that type of prior therapy, then that patient cannot be enrolled until September 8th.

Important note: The eligibility criteria listed below are interpreted literally and cannot be waived (per COG policy posted 5/11/01). All clinical and laboratory data required for determining eligibility of a patient enrolled on this trial must be available in the patient's medical or research record which will serve as the source document for verification at the time of audit.

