- h. XRT/External Beam Irradiation including Protons: ≥ 14 days must have elapsed after local XRT; ≥ 150 days after TBI, craniospinal XRT or if radiation to $\geq 50\%$ of the pelvis; ≥ 42 days if other substantial BM radiation.
- i. Radiopharmaceutical Therapy (e.g., radiolabeled antibody, 131I-MIBG): ≥ 42 days must have elapsed from the last dose of systemically administered radiopharmaceutical therapy.
- j. HDAC Inhibitors: Patients must not have received prior therapy with entinostat. Patients who have received therapy with other HDAC inhibitors are eligible.

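### The CNS response rules omit the protocol's own progression-since-radiation condition for measurable lesions, so shrinkage after recent local radiation can be scored as response or stable disease

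*Combined protocol and SAP*

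**What the plan says.** Section 12 of the protocol holds four sets of response rules.

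- **12.2, solid tumors under RECIST.** The note in 12.2.2.1 reads "Tumor lesions that are situated in a previously irradiated area must show definitive evidence of progression to be considered measurable".
- **12.3, evaluable disease.** It has no condition on radiation.
- **12.4, MIBG-positive neuroblastoma.** 12.4.1 covers one case only. If the patient's sole positive lesion was irradiated, "a biopsy must be done at least 28 days after radiation was completed and must show viable neuroblastoma".
- **12.5, CNS tumors.** 12.5.1 defines measurable disease as "Any lesion that is at minimum 10 mm in one dimension on standard MRI or CT, for CNS tumors". 12.5.3 makes a sole mass the target and otherwise allows up to 5 targets, chosen by size and suitability for repeat measurement. Nothing in 12.5.1 to 12.5.7 mentions prior radiation or points back to 12.2.2.1.

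Four provisions fix the timing:

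- Section 4.1.8.h sets the minimum interval before enrollment: "14 days must have elapsed after local XRT", with longer intervals for wider fields ("150 days after TBI, craniospinal XRT").
- Section 3.9: "The date protocol therapy is started must be no later than five (5) calendar days after the date of study enrollment".
- Section 4.0: "Imaging studies must be obtained within 14 days prior to start of protocol therapy".
- Section 8.1 puts the first disease evaluation at the end of Cycle 1.

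**The concern.** A lesion irradiated shortly before baseline may still be changing because of that radiation. The protocol recognizes this for solid tumors under 12.2 but leaves the condition out of the set used to score CNS tumors, and gives no reason for the difference. With a single arm, there is no comparison to separate continuing radiation effect from entinostat effect.

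What is at stake is aim 1.2.1, the preliminary description of antitumor activity. Shrinkage carried over from radiation can enter the CNS results as partial response or stable disease. A second effect runs the other way: enlargement after radiation can be scored as progression, which is a ground for removal under 10.1(a).

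There is also a mismatch of references. Section 4.1.5 sends all patients, CNS patients included, to 12.2 and 12.3 for the definitions of measurable and evaluable disease, and does not cite 12.5. The same irradiated CNS lesion can therefore be non-measurable when entry is judged and a target lesion when response is scored.

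**Working it through.** The plan gives no figure to reproduce here. The check is date arithmetic on the plan's own windows, a conversion of its thresholds, and a reading of the tables.

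**Timing at the minimum interval after local radiation (day 0 = last radiation)**
- Enrollment: day 14 (4.1.8.h).
- First dose: 0 to 5 days later (3.9), so day 14 to day 19.
- Baseline imaging: 0 to 14 days before the first dose (4.0). Earliest 14 - 14 = day 0; latest day 19.
- End-of-Cycle-1 scan: 14 + 28 = day 42 to 19 + 28 = day 47.
- Confirmatory scan one 28-day cycle later (8.1, footnote 4): day 70 to day 75.

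**CNS thresholds per diameter (12.5.4, both diameters changing equally)**
- Partial response, product down 50%: 1 - sqrt(0.5) = 0.293, or -29.3%. A 10 mm lesion falls to 7.1 mm and a 30 mm lesion to 21.2 mm.
- Progression, product up 25%: sqrt(1.25) - 1 = 0.118, or +11.8%. A 10 mm lesion grows to 11.2 mm. 12.5.4 has no absolute minimum, whereas 12.2.4.1 asks for 5 mm. That difference is a separate matter and applies to every CNS target, irradiated or not.
- Shrinkage short of -29.3% per diameter is scored as stable disease.

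**Effect of one misattributed response**
Section 11.1 plans 6 patients at each of 2 dose levels plus up to 6 for pharmacokinetics, that is 12 to 18. Assume all are evaluable for response.
- 1/12 = 8.3%.
- 1/18 = 5.6% (exact 95% CI 0.1% to 27.3%).

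**Would copying the 12.2.2.1 note into 12.5.1 be enough?**
- 12.5.2 and 12.3.1 both define evaluable disease as having no accurately measurable lesion. A sole 20 mm irradiated CNS lesion that has not progressed would then be neither measurable nor evaluable. Section 4.0 says the criteria are read literally, so that patient could fail 4.1.5. Section 12.5.3 says most CNS tumors present as one mass, so this is not a remote case.
- Every row of the 12.5.7 table takes a target-lesion status. A patient with only non-target disease could use just the last two rows, where that status is left open, and both give progression. Such a patient has no row for complete response or stable disease. Table 2 in 12.2.5 supplies such rows for other tumors.
- 12.5.4 counts progression in any established lesion, and 12.5.5 counts unequivocal progression of a non-target lesion. Moving the lesion to non-target raises the bar for progression but does not close that route.

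**The case against.** Several points on the other side have weight.

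- **The 12.2 note may already apply.** Section 4.1.4 treats CNS tumors as solid tumors, and 4.1.5 sends everyone to 12.2. This stands for entry at most. CNS response is scored under 12.5, whose own definition covers any lesion of the stated size.
- **Patients must have recurrent or refractory disease.** That narrows the case. But 4.1.4 describes the patient's disease and does not require the target lesion to have progressed since its latest radiation.
- **Safeguards exist.** Best response of PR or CR needs confirmation (12.6), and responders and patients stable for at least 6 cycles go to central review (8.2.1). Both help in part. The confirmatory scan, at about 70 to 75 days, is compared with the same baseline, and central review has no CNS irradiation rule to apply. Shorter stable disease and progression are not sent to central review.
- **Response is secondary.** Section 11.5 calls these analyses descriptive and exploratory, and the MTD rule uses dose-limiting toxicity only. This stands and limits the severity.

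A reader might infer that CNS tumors are the only set without protection. The documents do not support that: only 12.2 has a general lesion-level rule, 12.3 has none, and 12.4.1 covers a single situation. A reader might also take 14 days as the interval after any CNS radiation. It applies to local fields; craniospinal radiation needs 150 days and other substantial marrow radiation 42 days.

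**Conclusion.** The gap is real and should be closed, as a cheap improvement to a secondary aim. As written, 12.5 allows a CNS lesion irradiated as little as 0-19 days before baseline to be a target, with no evidence that it has progressed since. Continuing shrinkage can then be scored as response or stable disease.

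The size rests on two assumptions: local radiation at the minimum interval, and 12 to 18 response-evaluable patients. On those, one misattributed response moves the reported rate by 5.6 to 8.3 percentage points.

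Two stronger readings should be resisted. The first is that such misattribution will be common. The documents give neither the number of CNS or recently irradiated patients nor whether radiation change at these times reaches -29% per diameter. The second is that a lesion rule would also cure false progression. It would reduce it only in part, for the reason shown from 12.5.4 and 12.5.5.

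**What to change.** For response scoring only:

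1. In 12.5.1 and 12.5.3, state that a CNS lesion in a previously irradiated area is a measurable target only if it has shown definitive progression since that radiation.
2. In 12.5.2, state that a lesion failing this condition counts as evaluable disease even if its size can be measured, so that eligibility under 4.1.5 is unchanged.
3. Add rows to the 12.5.7 table for patients with non-target disease only, on the pattern of Table 2 in 12.2.5.
4. Reconcile 4.1.5, which cites 12.2 and 12.3 but not 12.5, so that entry and scoring use the same definitions for CNS patients.

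The cost is a few sentences and some table rows. No added study scan, reader or change in sample size is needed. The downside is that a few CNS patients leave the measurable-disease response group. The radiation interval in 4.1.8.h and the removal criteria in 10.1 are not touched.
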